5.0 EVALUATION OF OUTCOMES

5.1 Primary Outcomes

Following the successful implementation of immunologic (ELISPOT) and virologic (viral load measurements) assays at NARI (See quality control and training details above), this project will collect data to address the two stated primary objectives.

5.1.1. Primary Objective (a).

To compare initial CD8-mediated immune response with HIV-1 viral set point

The initial research hypothesis for this objective, based upon prior US-based studies of individuals infected with HIV-1 subtype B, is that HIV-1-infected individuals with early CD8⁺-mediated recognition of multiple HIV-1-gag epitopes (polyclonal response) will demonstrate a lower HIV-1 viral set point, compared with individuals that do not recognize multiple HIV-1 gag epitopes. A further hypothesis is that this correlation will be demonstrated in recently infected individuals across diverse populations infected with different strains of HIV-1. The primary outcome measures for this analysis will be HIV-1 viral set point, defined as the median viral load between 6 and 12 months after estimated time of primary infection, and quantification of the number of different HIV-1 gag peptides recognized by each individual, as measured in an ELISPOT assay. In cases where positive responses are detected in the initial screen of the ELISPOT assay, additional assays will be performed on stored specimens to determine the phenotype of the responding cell, epitope specificity and MHC restriction. Based upon this initial analysis of gag-responses and upon data from other ongoing studies, we propose to consider expanding this ELISPOT analysis to include assessment of recognition of other HIV-1 antigens, including env, nef and tat.

5.1.2 Primary Objective (b).

To compare host immunologic genetic characteristics with HIV-1 viral set point.

The initial research hypothesis for this objective, based upon prior studies in a few countries demonstrating that certain HLA class I alleles may be associated with a slower disease HIV-1 progression, is that there are specific host genetic characteristics that will be associated with a lower HIV-1 viral set point in individuals from non-North American populations

infected with different strains of HIV-1. The primary outcome measure for this analysis will be HIV-1 viral set point, defined above, and HLA class I allelic genotype. Based upon this initial analysis of the HIV-1 class I alleles and upon data from other ongoing studies, we propose to consider expanding this analysis to include assessment of HLA Class II alleles and co-receptor genotyping.

5.1.3 Primary Endpoints

(a) Median HIV-1 viral load between 6 and 12 months after estimated time of primary infection

(b) ELISPOT measurement of HIV-1 peptide-specific T lymphocytes

(c) HLA-Class I MHC alleles

5.2 Secondary Outcomes

This protocol will also address a number of secondary objectives.

5.2.1 Secondary Objectives (a)

To characterize the epitope specificity of the initial CD8-mediated immune response.

For subjects demonstrating a response to HIV-1-gag peptides, the NARI site will be provided an opportunity to further characterize the HLA-restriction and minimal peptide epitopes of these responses.

5.2.2 Secondary Objective (b)

To provide immunological and virological laboratory training and to establish laboratory quality control procedures for the NARI HPTU.

Assessment of on-site capability to perform HIV-1 viral load and ELISPOT analyses will include participation in the quality control procedures outlined above.

5.2.3 Secondary Objective (c)

To assess the feasibility of establishing a prospective cohort of recently infected individuals and their primary sexual partners for participation in HPTN HIV-1 prevention trials of discordant couples.

This laboratory study will provide an opportunity to assess the feasibility of establishing and following cohorts of recently infected individuals and their sexual partners for future HPTN trials. Therefore enrollment and retention rates will be enumerated and evaluated.

5.2.4 Secondary Objective (d)

To establish a repository of plasma and PBMC specimens from recently HIV-1infected individuals, for future HPTN and collaborative immunologic and virologic studies.

Remaining plasma and PBMC specimens from study participants will be reposited on-site and provide opportunities for HPTN and non-HPTN investigators to propose additional site specific and collaborative laboratory studies in the future.

5.2.5 Secondary Endpoints:

(a). Characterization of MHC Class I restriction and minimal HIV-1 peptide sequence of viral-specific T lymphocytes in early HIV-1 infection.

Quality control assessment of HIV-1 viral load and ELISPOT assays at the Pune site.

(b). Measurement of enrollment and retention of study participants (and their primary partners, if enrolled in the HPTN 034B Exposed-Uninfected Sub-study)

6.0. DATA COLLECTION

6.1 Data Forms

Data will be collected on standardized forms to be outlined in the site-specific procedures manual. An appropriate system for data transfer from the sites to the HCL and for central data management, quality assurance and analysis will be developed and utilized. Data and care report forms flow chart will be included in the study specific procedures manual along with procedures for data collection, transfer, and management.

6.2 Record Storage and Archive

The study site principal investigator and laboratory personnel will maintain all source documents used to complete case report forms including laboratory requisitions and reports, documentation of referrals, and progress notes. Specimens will be tracked using the Laboratory Data Management System (LDMS). All data collection forms and source records must be kept in locked files in a secure area. All study documents with participant identifying information including locator information and informed consent forms must be kept in locked files in a secure area apart from all other study documents. Study records must be available at all times for review by FHI, the study sponsor (NIAID) or their agents.

6.3 Statistical Considerations and Sample Size Calculations

Based upon assumptions outlined below for each of the two primary objectives, the target samples size for this study is a minimum of 20 subjects with recent HIV-1-infection retained for at least 1 year of follow-up. For both primary objectives, HIV-1 viral set point will be an outcome measure. Subjects will be stratified according to median viral load measured between 6 and 12 months after estimated time of primary infection (See Table 1. viral set point=median VL

of visits 5-8). Based upon this calculation, subjects would be stratified into the following categories: <10000 copies/ml, 10000-75000 copies/ml, >75000 copies/ml.

6.3.1 Primary Objective (a).

Gag-specific ELISPOT Response vs. HIV-1 Viral Set Point.

For the purposes of comparing ELISPOT response to viral load set point, gag-specific ELISPOT responses will be stratified into two categories: Responses recognizing two or fewer HIV-1 gag peptides and those responses recognizing more than two different HIV-1 gag peptides. As outlined in Appendix E, all experiments will be performed in duplicate wells. The IFN- γ -expressing spots will be calculated as the number of spots per 100,000 stimulated PBMCs. Results will be expressed as net peptide-specific IFN- γ spots / 10⁵ PBMC. A positive peptide-specific response (responders) will be defined as a mean of greater than 5 spots above the mean spots of the mock-stimulated PBMC. Study participants will be expected to have multiple ELISPOT assays within the first 12 months of follow-up (See Appendix A).

This is a descriptive sub-study proposed for HPTN 034. Therefore, it is not expected that we will have sufficient sample size to definitively address the primary endpoint. Never the less, we will undertake the analysis as outlined on our projected sample size of 20-30 individuals. However, we have also projected that data from this sub-study would also be available for combining with similar data from other HPTN protocols in the future. Our subsequent "meta-analysis" will compare HIV-1 viral set point with the recognition of more than two (>2) gag peptides at any time point within 12 months since estimated time of infection. Separate and similar analyses will be performed for recognition of HIV-1 subtype B gag and non-B gag peptides. Additional analyses will determine if other ELISPOT outcome measures, such as consistent recognition of more than 2 gag peptides at multiple time points, also correlate with viral set point. We predict a 30% difference between the groups with respect to the proportion of individuals who elicit a broad immunologic response (defined above). With a sample size of n=39 per arm from multiple HPTN protocols in the future, we will have 80% power to detect a 30% difference (p=0.05).

Percent ELISPOT response to >2 HIV-1 gag peptides			Estimated Sa	mple Size
<10000 RNA	10000-75000 RNA	>75000 RNA	N per arm	Total N
copies/ml	copies/ml	copies/ml		
70%	50%	30%	93	279
80%	50%	20%	39	117
90%	50%	10%	20	60

Sample Size Estimate

6.3.2 Primary Objective (b).

HLA Class I alleles vs. HIV-1 Viral Set Point.

A similar "meta analysis" of data from 034A and other similar sub-studies is anticipated for this objective. The proportion of individuals with specific HLA Class I alleles will be compared with the viral load set point. Using HLA A2 as an example (known to be associated with a frequently measurable immune response to gag peptides), we posit that a higher percentage of individuals with this allele will fall into the low viral set point category. Again, we will have an 80% power to detect a 30% difference in the proportion of individuals with HLA A2 given a sample size of 39 individuals per arm.

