4.2 Enrollment

Enrollment will take place over the two years of the HPTN 034 protocol; participants will be followed for up to two years, if funding is available. The schedule for sample collection is outlined in Table 1. If it can be determined that participants were infected within the previous three months, samples would be drawn at enrollment, once a month for three months, and then every three months for up to two years. If participants have been infected for more than three months, and less then six months, specimens would be collected at enrollment, and every three

months for up to two years. Participants will be asked to provide a 40 ml blood sample (four EDTA vacutainer tubes, 10mls/tube), answer a short questionnaire and undergo a brief physical exam. PBMC and plasma will be stored on site for immunologic and virologic studies through the CL.

Study participants with recent HIV-1 infection will be also be strongly advised to refer their primary sexual partner(s) for HIV-1 screening and risk reduction counseling. Sexual partners of participants with recent HIV-1 infection who agree to HIV-1 screening will be determined to be either chronically HIV-1 infected of unknown duration, recently HIV-1 infected themselves, or HIV-1-uninfected. Those partners found to be recently HIV-1-infected will also be eligible for enrollment in this study. Partners found not to be HIV-1 infected will be eligible to enroll in a companion HPTN sub-study of exposed-uninfected partners (HPTN 034B).

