APPENDIX A

Table 1. Scheduled visits for acute seroconvertors

	Screening	Enrollment														
Month	Pre	0	1	2	3	6	9	12	15	18	21	24	27	30	33	36
Study Visit	01	02	03	04	05	06	07	08	09	10	11	12	13	14	15	16
Patient ID	Х	Х	Х	Х	Х	Х	Х	Х	Х	Х	Х	Х	Х	Х	Х	Х
Physical Exam	Х	Х	Х	Х	Х	Х	Х	Х	Х	Х	Х	Х	Х	Х	Х	Х
Questionnaire	X	X	X	Х	Х	X	X	X	X	X	X	X	X	X	X	Х
Assays:																
HIV-1 Test ¹	Х															
HIV-1 RNA PCR (VL)	Х	Х	Х	Х	Х	Х	Х	Х	Х	Х	Х	Х	Х	Х	Х	Х
Storage:																
Plasma		Х	Х	Х	Х	Х	Х	Х	Х	Х	Х	Х	Х	Х	Х	Х
PBMC		Х	Х	Х	Х	Х	Х	Х	Х	Х	Х	Х	Х	Х	Х	Х
HLA Typing		Х														
Total blood volume (ml)	10	40	40	40	40	40	40	40	40	40	40	40	40	40	40	40
Number of tubes ²	1	4	4	4	4	4	4	4	4	4	4	4	4	4	4	4

¹Assay (PCR, ELISA, detuned assay will be site-specific) ²Tubes will be 10ml lavender top tubes containing EDTA.

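### 034A section 6.3 gives two incompatible rules for viral set point: 6-12 months after infection, and visits 5-8, which span nine months from enrolment

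*Supplement*

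**What the plan says.** The 034A protocol summary, section 5.1.1 and section 5.1.3 all tie set point to time since infection. Section 5.1.1 has "HIV-1 viral set point, defined as the median viral load between 6 and 12 months after estimated time of primary infection", and primary endpoint (a) in section 5.1.3 is "Median HIV-1 viral load between 6 and 12 months after estimated time of primary infection".

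Section 6.3 repeats this in its main clause, "Subjects will be stratified according to median viral load measured between 6 and 12 months after estimated time of primary infection", and then adds a parenthesis: "See Table 1. viral set point=median VL" "of visits 5-8). Based upon this calculation, subjects would be stratified into the following categories". The categories are below 10,000, 10,000-75,000 and above 75,000 copies/ml.

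Appendix A, "Table 1. Scheduled visits for acute seroconvertors", has the month row "Month Pre 0 1 2 3 6 9 12 15 18 21 24". Month 0 is the enrolment column (visit 02), so visits 05, 06, 07 and 08 stand at months 3, 6, 9 and 12. Section 4.2 also counts sampling from enrolment. People infected less than three months earlier are sampled monthly for three months and then quarterly. For those infected three to six months earlier, "specimens would be collected at enrollment, and every three" months.

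Section 2.3 admits participants whose infection is documented within the past six months. The 2004 Letter of Amendment and the clarification memos leave the set-point rule and the viral-load visits unchanged.

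**The concern.** The two rules use different clocks, one starting at infection and the other at enrolment, and windows of different length. They select different readings, yet the plan presents them as the same quantity. An analyst who follows the parenthesis will include viral loads from outside the stated endpoint window. Which ones depends on how soon after infection the person was enrolled: readings before month 6 in people found early, and after month 12 in all but those enrolled at infection.

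Set point assigns participants to the three bands on which the planned 034A comparisons and the sample-size table are built. Section 6.3.1 also expects the data to be combined later with similar data from other HPTN protocols, so an unresolved definition would pass into that pooled analysis.

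**Working it through.** **The plan's own figure.** The only design number resting on the set-point bands is the n per arm in section 6.3.1. The formula is the comparison of two proportions with pooled variance, two-sided 0.05, power 80%, no continuity correction:

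n = [1.960·√(2p̄q̄) + 0.842·√(p₁q₁ + p₂q₂)]² / (p₁ − p₂)²

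For 80% against 50%: [1.960·√0.455 + 0.842·√0.41]² / 0.09 = (1.322 + 0.539)² / 0.09 ≈ 38.5, so 39. The same formula gives 93 for 70% against 50% and 20 for 90% against 50%. All three match the plan and do not depend on which set-point rule is used.

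**Inputs for the timing check**
- Window: 6 to 12 months after infection, both ends included (5.1.1, 5.1.3, 6.3).
- Visits 5-8: months 3, 6, 9 and 12 after enrolment (Table 1).
- Lag t from infection to enrolment: 0 to 6 months (2.3).

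**Width.** The four visits span 12 − 3 = 9 months; the window is 12 − 6 = 6 months wide. All four cannot fit.

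**How many fit.** Visits 5-8 fall at t+3, t+6, t+9 and t+12 months after infection. For t between 0 and 6:
- visit 5 is inside when t ≥ 3;
- visit 6 is always inside;
- visit 7 is inside when t ≤ 3;
- visit 8 is inside only when t = 0.

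| Lag t (months) | Visits 5-8, months after infection | Inside 6-12 |
|---|---|---|
| 0 | 3, 6, 9, 12 | 3 of 4 |
| 1.5 | 4.5, 7.5, 10.5, 13.5 | 2 of 4 |
| 3 | 6, 9, 12, 15 | 3 of 4 |
| 4 | 7, 10, 13, 16 | 2 of 4 |
| 6 | 9, 12, 15, 18 | 2 of 4 |

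A count over t = 0 to 6 in steps of 0.01 month finds three of four only at t = 0 and t = 3, and two of four at the other 599 values.

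**Other readings of the text**
- If Table 1's months meant months since infection, visit 5 would be at month 3, still outside.
- If the quarterly-only group were numbered consecutively, its visits 5-8 would fall at months 9, 12, 15 and 18 after enrolment. For t above 3, none would be in the window.
- Borrowing the parent study's 22-day visit tolerance at both ends shortens the span to 9 − 44/30.4375 ≈ 7.6 months, still more than 6.

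**What a date-based rule would have to work with.** On the section 4.2 schedules, the in-window samples are those at t+6 and t+9 for lags between 0 and 3 months, and at t+3 and t+6 for lags between 3 and 6. That is two readings; a third appears only at lags of exactly 0, 3 or 6. If a minimum of two were imposed, one missed visit would remove a participant. At an assumed 90-95% attendance per visit, 1 − 0.90² = 19% to 1 − 0.95² ≈ 10% would be lost. If one reading suffices, the loss is 0.10² = 1% to 0.05² = 0.25%.

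**The case against.** The infection-based definition appears in the summary, 5.1.1, 5.1.3 and the main clause of 6.3, while the visit rule appears once, in brackets. A sensible analyst might treat the bracket as a slip, perhaps for visits 6-8. This stands as a reason for knowing which rule to keep. It does not remove the contradiction, and visits 6-8 would still run past month 12 for anyone enrolled after infection.

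Section 6.3.1 calls 034A descriptive and does not expect its 20-30 participants to settle the primary endpoint. Table 1 schedules viral load at every visit, so either rule can be applied later without loss of data. Both points stand, and they limit the urgency.

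Three stronger readings are tempting, and the documents do not support them.

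- **That the outcome is valid for no participant.** Only the complete four-visit set can never fit. Two or three readings always do, the two medians may coincide, and someone who missed the out-of-window visits would comply by accident.
- **That the share of people changing band measures bias.** With values not in the documents (lag uniform over 0-6 months, mean 4.5 log10, between-person SD 0.8, reading SD 0.3), about 10% change band between the two rules. The share is 10.0% with no early viral excess and 10.1% with an excess of 0.5 or 1 log10. It is essentially measurement noise from taking medians over different readings.
- **That enrolment timing links exposure and outcome for both objectives.** In objective (b) the exposure is HLA class I genotype, which timing cannot alter. In objective (a) the planned pooled analysis counts recognition of more than two gag peptides at any time within 12 months of estimated infection, so the exposure is anchored to infection. Sampling intensity may still vary with lag, but neither the direction nor the size of any link is established.

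**Conclusion.** The contradiction holds as a matter of arithmetic, using only the stated window, Table 1 and the six-month eligibility limit. Followed literally, the visit rule brings in one out-of-window reading of four at lags of exactly 0 or 3 months and two of four at every other lag, and its span moves from months 3-12 to months 9-18 as enrolment comes later. The counts assume visits on their scheduled dates and an infection date known exactly.

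The effect on 034A's results cannot be sized from the documents. The defect is a wrong operational rule for a primary outcome, cheap to correct. It is not evidence of a biased finding, it leaves the n of 39 per arm alone, and it does not touch the parent study's incidence or retention endpoints.

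**What to change.** - In 034A section 6.3, delete the parenthesis beginning "See Table 1. viral set point=median VL". Define set point as the median of all viral loads dated 6-12 months after the estimated infection date, both ends included, whatever the visit number.
- Keep participants with a single in-window reading in the main analysis. Report how many there are, and check the result without them in a sensitivity analysis.
- State how the infection date is estimated for each entry route in section 3.1. The midpoint between last negative and first positive test suits documented seroconverters only. Participants entering by PCR or p24 antigen, and those entering by detuned ELISA, need their own stated rule.
- Use the same definition for 034B secondary endpoint (a), where infection occurs during follow-up and visit numbers bear no fixed relation to it.

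The cost is a few sentences and selection by date in the analysis program. No visits or assays are added in 034A, since viral load is already scheduled at every visit, and the sample size does not change. The price is that most participants will have a median of two readings instead of four, so set point will be somewhat less precise.

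### 034A defines viral set point as 6-12 months after infection but computes it from visits 5-8, which fall 3-18 months after infection

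*Supplement*

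**What the plan says.** The 034A protocol defines the endpoint in section 5.1.3 as "Median HIV-1 viral load between 6 and 12 months after estimated time of primary infection". The Protocol Summary and section 5.1.1 give the same window.

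Section 6.3 repeats the window and in the same sentence gives the computing rule: "median viral load measured between 6 and 12 months after estimated time of primary infection (See Table 1. viral set point=median VL". The sentence then names visits 5-8 as the source of that median. Participants are sorted by the result into three bands: below 10,000, 10,000-75,000 and above 75,000 copies/ml. Section 6.3 also says that set point is an outcome measure for both primary objectives.

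The table referred to is "Table 1. Scheduled visits for acute seroconvertors" in Appendix A. Its first two rows read "Month Pre 0 1 2 3 6 9 12" and "Study Visit 01 02 03 04 05 06 07 08". Month 0 stands under the enrolment heading, so visits 05, 06, 07 and 08 are months 3, 6, 9 and 12 after enrolment.

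Sections 2.3 and 3.1 admit people with infection documented within the past six months. Section 4.2 counts blood draws from enrolment: monthly for three months and then quarterly for those infected less than three months before, and quarterly throughout for those infected three to six months before.

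**The concern.** The definition runs on a clock that starts at estimated infection. The visit rule runs on a clock that starts at enrolment. The two differ by each participant's time from infection to enrolment, which the eligibility criteria allow to be anything up to six months. No single set of four consecutive quarterly visits can match a six-month window for everyone.

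Two things are at stake. First, the primary outcome as computed is not the primary outcome as defined, and a programmer following section 6.3 would have to choose between them. Second, the mismatch is not the same for all participants: the later someone enrols, the later the period that the median summarises. If viral load changes over months 3-18, part of the difference in set point between participants would reflect when they enrolled.

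The issue reaches beyond Pune. Section 1.0 of 034A intends its procedures and schedules to be applied consistently in other HPTN protocols, with a view to a meta-analysis, so the rule would be carried forward.

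**Working it through.** **Inputs**
- Window W: 6 to 12 months after estimated infection (034A sections 5.1.1, 5.1.3 and 6.3).
- Visits 5-8: months m = 3, 6, 9, 12 after enrolment (Appendix A, Table 1).
- Time from infection to enrolment, t0: 0 to 6 months (sections 2.3 and 3.1).
- Assumption: t0 uniform on 0-6 months. The documents give no distribution.

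The plan gives no figure for the share of readings inside the window. Its figures that use the set-point bands are the sample sizes in section 6.3.1, and these reproduce. For 80% against 50% in adjacent bands (two-sided 0.05, 80% power, no continuity correction), n = [1.96·√(2·0.65·0.35) + 0.8416·√(0.16 + 0.25)]² / 0.30² = (1.322 + 0.539)² / 0.09 = 38.5, so 39 per band and 3 × 39 = 117 in total. The problem is not in that arithmetic.

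**Step 1. Time since infection at each reading: t0 + m**

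| t0 (months) | Visit 5 | Visit 6 | Visit 7 | Visit 8 | Readings in W |
|---|---|---|---|---|---|
| 0 | 3 | 6 | 9 | 12 | 3 |
| 1 | 4 | 7 | 10 | 13 | 2 |
| 2 | 5 | 8 | 11 | 14 | 2 |
| 3 | 6 | 9 | 12 | 15 | 3 |
| 4 | 7 | 10 | 13 | 16 | 2 |
| 5 | 8 | 11 | 14 | 17 | 2 |
| 6 | 9 | 12 | 15 | 18 | 2 |

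The range is 3 to 18 months. Two of four readings are in W for every t0 except exactly 0 and exactly 3 months.

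**Step 2. Share of readings in W, t0 uniform on 0-6**
- Visit 5 (t0 + 3): in W if t0 ≥ 3, so 50% in and 50% early.
- Visit 6 (t0 + 6): always in W, 100%.
- Visit 7 (t0 + 9): in W if t0 ≤ 3, so 50% in and 50% late.
- Visit 8 (t0 + 12): in W only at t0 = 0, so 0% in and 100% late.

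In: (0.5 + 1 + 0.5 + 0)/4 = 50%. Early: 0.5/4 = 12.5%. Late: (0.5 + 1)/4 = 37.5%.

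**Step 3. Early against late enrollees**
- 0 < t0 < 3: visit 5 is early, visits 6 and 7 are in, visit 8 is late.
- 3 < t0 ≤ 6: visits 5 and 6 are in, visits 7 and 8 are late.

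The mean reading time under the visit rule is t0 + (3 + 6 + 9 + 12)/4 = t0 + 7.5. With mean t0 of 1.5 and 4.5 months in the two groups, that is 9 and 12 months after infection, a gap of three months.

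**Step 4. The same under selection by date**
From the section 4.2 schedule, the samples in W are months 6 and 9 for t0 < 3 and months 3 and 6 for t0 > 3. Mean times are 1.5 + 7.5 = 9 and 4.5 + 4.5 = 9 months. The gap disappears, and each participant has two readings.

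**Step 5. Alternative reading of Table 1**
If its months were meant to run from infection, month 3 would still be outside W, so one reading in four would be wrong. The enrolment heading over month 0 and section 4.2 both speak against that reading.

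**The case against.** **Four readings beat two.** If viral load is already flat by month 3 and stays so to month 18, visits 5-8 estimate the same quantity with less noise. This stands as far as it goes. Assume a true set point of 4.5 ± 0.7 log10, within-person SD 0.3 and no time trend. Simulation then puts 12.1% of participants in the wrong band with visits 5-8 and 15.6% with in-window readings only. But a flat course is an assumption that the documents do not make, and they define a window instead. The cost should be stated; it does not remove the contradiction.

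**034A is descriptive.** Section 6.3.1 says that 20-30 people are not expected to settle the primary endpoint. That answers a complaint about power. It does not answer an outcome defined in two incompatible ways, and the protocol still undertakes the analysis on those people and plans to pool the data.

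**Stronger readings.** A reader might infer that cutting set point into three bands loses most of the power. The documents do not support this. No test is named for the three-band comparison, so a chi-square on the two-by-three table cannot be treated as the plan's method. The cost of banding viral load alone is modest. With normal log10 values, band limits at the terciles and response rates of 80/50/20%, three equal bands keep 79% of the information. Power falls from 69% to 61% at N = 20 and from 88% to 81% at N = 30 when a trend test across the bands is used.

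A reader might also infer that a known share of participants would change band because of the out-of-window visits. Under the no-trend model above, about 11% do change band between the two medians. That is only sampling noise between a four-reading and a two-reading median, not evidence of bias.

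**Conclusion.** The definition and the computing rule in 034A section 6.3 contradict each other and must be reconciled. The readings named in the rule span 3-18 months after infection, against a defined window of 6-12. Two of four lie outside it for essentially every participant.

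That count needs only Table 1 read as headed (month 0 = enrolment), visits numbered as in that table, and enrolment 0-6 months after infection. The 50 / 12.5 / 37.5% split and the three-month gap between early and late enrollees also need enrolment spread evenly over 0-6 months.

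The effect on the estimated association with ELISPOT response or HLA type is unknown: the documents give neither a viral-load trajectory nor a within-person variance. The point concerns which period the outcome measures. It does not extend to a large loss of power, and the choice of bands in a sub-study that calls itself descriptive is not an error.

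**What to change.** In 034A section 6.3, replace the visit 5-8 rule with the median of all viral loads dated 6-12 months after the estimated infection date. State the minimum number of readings required, and state or point to the rule that sets the estimated infection date, since the existing definition already depends on it. Write the same rule into the planned pooled analysis, so that other HPTN protocols do not copy the visit numbers. The Protocol Summary and sections 5.1.1 and 5.1.3 already carry the window and need no change.

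The cost is a wording change with no new samples. Essentially every participant, early or late, contributes two readings instead of four, so each median is somewhat noisier. The median of visits 5-8 can be kept as a sensitivity analysis, which would also show how far the two rules disagree in practice.

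An additional analysis of continuous log10 set point against the number of gag peptides recognised is optional.
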